8.1.2 Tumor imaging during the study

The first on-study scan assessment should be performed at 6 weeks (± 2 weeks; starting from cycle 1 day 1). Subsequent tumor scans should be performed every 6 weeks (± 2 weeks).

All supplemental imaging must be collected.

Objective response should be confirmed by repeat scan performed at least 4 weeks after the first indication of a response is observed. Patients will then return to the regular scan scheduled, starting with the next scheduled time point. Patients who receive additional scans for confirmation do not need to undergo the next scheduled scan if it is fewer than 4 weeks later; scans may resume at the subsequent scheduled time point.

When radiological disease progression is identified by the investigator in clinically stable patients, disease progression is to be confirmed by another set of scans performed 4 to 8 weeks later, per iRECIST guidelines in section [8.1.5](#).

If disease progression is not confirmed, clinically stable patients are to continue study interventions until progression is confirmed. Patients are to return to their regular scan schedule. If the next scheduled scan will occur in less than 4 weeks, this scheduled scan may be skipped.

If disease progression is confirmed, study interventions will be discontinued. Exceptions are detailed in section [8.1.5](#).

8.1.3 End of treatment and follow-up tumor imaging

If patients discontinue study interventions, tumor scans should be performed at the time of discontinuation (± 4 -week window) unless previous scans were obtained within 4 weeks of discontinuation.

If patients discontinue study interventions without documented disease progression, every effort should be made to monitor disease status by acquiring tumor scans using the same schedule used while on treatment (every 6 weeks [± 2 weeks]).

Scans are to be continued until:

- Confirmed disease progression per iRECIST

- Start of next-line anti-cancer treatment
- Pregnancy of the patient
- Withdrawal of consent by the patient
- End of the study

All imaging assessments need to have confirmatory imaging using the identical method after at least 4 weeks.

Patients who are clinically stable and treated past radiographic progression may continue to be assessed until progression is confirmed according to the rules of iRECIST, when clinically appropriate.

8.1.4 RECIST 1.1 assessment of disease

RECIST 1.1 will be used as the primary measure for assessment of tumor response, date of disease progression, and as a basis for all Protocol guidelines related to disease status (e.g., discontinuation of study interventions).

8.1.5 iRECIST assessment of disease

iRECIST is based on RECIST 1.1 but adapted to account for the unique tumor response seen with immunotherapeutic drugs. iRECIST will be used by the investigator to assess tumor response and progression and make treatment decisions. When clinically stable, patients may continue study interventions beyond RECIST 1.1 progression with continued assessment of response according to the rules outlined in section 10.2. iRECIST reflects that some patients can have a transient tumor flare after the start of immunotherapy, then experience subsequent disease response. This data will be captured in the clinical database.

- If the patient is clinically stable, continue study interventions per Protocol
 - Perform scans 4 to 8 weeks after RECIST 1.1 progression
 - Continue investigator assessment per iRECIST
 - Collect scans
- If the patient is not clinically stable, best medical practice is to be applied

For the purpose of this decision process, lack of clinical stability is defined as:

- Unacceptable toxicity
- Clinical signs or symptoms indicating clinically significant disease progression
- Decline in performance status
- Rapid disease progression or threat to vital organs or critical anatomical sites (e.g., central nervous system metastasis, respiratory failure due to tumor compression, spinal cord compression) requiring urgent alternative medical intervention

8.2 Safety assessments

If patients feel unwell at any point in time during the study after being discharged from the hospital, they should contact their study investigator as indicated in the ICF.

8.2.1 Physical examinations, ECOG performance status, body height, and body weight

General physical examination with organ/system-specific physical examination will be carried out by a licensed physician (or the physician's assistant or a nurse practitioner).

For screening, a complete physical examination will be performed including head (eyes, ear, nose, and throat), neck, cardiovascular, chest/lungs, abdomen (including liver and spleen size), extremities, neurological, skin, and lymph nodes. For subsequent visits, a physical examination is to be done with the focus on abdomen (including liver and spleen size), lymph nodes, and any other system that may contribute to clinical disease assessments.

An ECOG performance status will be assigned, and body height and body weight will be measured.

8.2.2 Vital signs

Vital signs will include blood pressure (systolic and diastolic, after ≥ 5 minutes of rest), body temperature, and heart rate.

8.2.3 Special assessments on treatment days

8.2.3.1 Nanrilefusp alfa treatment days of cycles 1 to 3

Patients will be observed in the hospital up to 4 hours following nanrilefusp alfa administration. Vital signs (blood pressure [systolic and diastolic, after ≥ 5 minutes of rest], body temperature, and heart rate) will be documented at the following frequency until discharge:

- Before nanrilefusp alfa administration
- 15 minutes (± 5 minutes) after nanrilefusp alfa administration
- 30 minutes (± 5 minutes) after nanrilefusp alfa administration
- 2 hours (± 15 minutes) after nanrilefusp alfa administration
- 4 hours (± 30 minutes) after nanrilefusp alfa administration

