Serum for cytokines		X ¹⁹						X ^{19,20}						
Whole blood for exploratory biomarkers		X ^{11,21}						X ¹¹						
Survival status														X ²²
Next-line anti-cancer treatment														X ²²
Date of progression on next-line anti-cancer treatment														X

- * Criteria for discontinuation of study interventions are listed in section [7.1](#).
- ** Every 30 (± 2) days until 60 (± 2) days after the last dose of cetuximab or 30 (± 2) days after the last dose of nanrilkefusp alfa, whichever is later
- 1. No study-specific procedures are to be performed before Informed Consent Form signature
- 2. Age at screening and gender
- 3. Primary tumor location, histology/cytology, initial diagnosis date, lines of previous treatment, start and stop dates of the treatments before this study, any prior mutations/genetic analysis (e.g., EGFR, K-RAS/N-RAS mutations), and the date of the latest disease progression if not coinciding with the stop date
- 4. Within 7 days before day 1 of cycle 1
- 5. On the day of dosing before nanrilkefusp alfa administration and/or cetuximab administration
- 6. Sample can be taken within 24 hours before nanrilkefusp alfa and/or cetuximab administration
- 7. Before nanrilkefusp alfa administration and afterwards as clinically required
- 8. Follow-up visit 30 (± 2) days after the last dose of nanrilkefusp alfa and/or cetuximab (whichever occurs later)
- 9. Last body weight assessment within 3 days prior to day 1 should be used for dose calculation.
- 10. Before and after nanrilkefusp alfa administration as described in section [8.2.3](#)
- 11. Before nanrilkefusp alfa and/or cetuximab administration
- 12. Additional samples may be taken as clinically indicated
- 13. Before nanrilkefusp alfa administration and 2 hours (± 15 min) after nanrilkefusp alfa administration
- 14. Tumor scans performed as part of routine clinical management are acceptable for screening if they are of acceptable diagnostic quality and performed within 21 days prior to ICF signature
- 15. Time to be recorded
- 16. Time to be recorded; on day 1 and day 8, cetuximab infusion will start within 30 minutes after nanrilkefusp alfa administration
- 17. Contact 90 (± 2) days after the last dose of nanrilkefusp alfa and/or cetuximab (whichever occurs later)
- 18. To be collected up to cycle 4
- 19. Before nanrilkefusp alfa administration and 6 hours (± 15 min) after nanrilkefusp alfa administration
- 20. Only in cycle 2

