8.2.3.2 Nanrilefusp alfa treatment days of cycle 4 and onwards

Patients will be observed in the hospital up to 2 hours after nanrilefusp alfa administration. Vital signs (blood pressure [systolic and diastolic, after ≥ 5 minutes of rest], body temperature, and heart rate) will be documented at the following frequency until discharge:

- Before nanrilefusp alfa administration
- 15 minutes (± 5 minutes) after nanrilefusp alfa administration
- 30 minutes (± 5 minutes) after nanrilefusp alfa administration
- 2 hours (± 15 minutes) after nanrilefusp alfa administration

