4.1.2. Screening Period

For all patients, the screening period is defined as the period from time of signing ICF to the first dose of treatment (nanrilkefusp alfa or cetuximab) (before day 1 of cycle 1). For some variables, data from more than one assessment within the screening period can be collected prior to the first dose of treatment (nanrilkefusp alfa or cetuximab).

The baseline value is defined as the last non-missing value collected before the first dose of study treatment (nanrilkefusp alfa and/or cetuximab) in the screening period. However, for K-RAS and N-RAS parameters as well as eGFR mutation status which come from Biopsy performed within 3 months prior to first dose will also be considered as baseline values.

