5.6.6. Vital Signs

The analyses described below will be conducted for the following vital signs assessments respectively:

- SBP (mmHg);
- DBP (mmHg);
- Heart rate (bpm);
- Body Temperature ($^{\circ}\text{C}$)

The following will be summarized by overall for the ASaT population:

- Observed values and change from baseline at each scheduled assessed visit for each standard vital sign parameter using default summary statistics for continuous variables

A listing of all vital signs data including derived change from baseline will be provided for the screened population.

The actual values and CFB for each scheduled study visit for selected vital signs parameters will be plotted at each time point using a line plot including 95% CI bars around the mean, this will be done by overall for ASaT population.

Total counts and percentages of patients will be presented for the following:

- Maximum increase from baseline in SBP and DBP (mmHg):
 - <20
 - ≥ 20 and <40
 - ≥ 40 and <60
 - ≥ 60
- Maximum decrease from baseline in SBP and DBP (mmHg):
 - <20
 - ≥ 20 and <40
 - ≥ 40 and <60
 - ≥ 60
- Maximum increase from baseline in heart rate (bmp):
 - <30
 - ≥ 30
- Maximum decrease from baseline in heart rate (bmp):
 - <30
 - ≥ 30
- Maximum postdose heart rate (bmp)
 - <50
 - ≥ 50 and <120
 - ≥ 120

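### SAP 5.6.6 takes every vital-sign change from the single pre-first-dose baseline, so from cycle 1 day 2 its maximum rise and fall tables mix between-day drift with acute post-dose change; a same-day pre-dose comparison should be added

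*Protocol*

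**What the plan says.** Protocol 8.2.3 states that vital signs on nanrilkefusp alfa days "will be documented at the following frequency until discharge". The list for cycles 1 to 3 opens with a reading "Before nanrilefusp alfa administration" and ends with one "4 hours (± 30 minutes) after nanrilefusp alfa administration"; between them are readings at 15 minutes, 30 minutes and 2 hours. From cycle 4 the list stops at 2 hours: "Patients will be observed in the hospital up to 2 hours after nanrilefusp alfa administration". The footnote to the Schedule of activities (1.3) repeats the pattern: "Before and after nanrilkefusp alfa administration as described in section" 8.2.3. Dosing is on days 1, 2, 8 and 9 of each cycle (Protocol 6.1), and the schedule adds a vital-sign reading before cetuximab on day 15.

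SAP 4.1.2 sets one reference per patient: "The baseline value is defined as the last non-missing value collected before the first dose of study treatment". SAP 4.1.1 defines change as visit value minus that baseline. SAP 5.6.6 then summarises "Observed values and change from baseline at each scheduled assessed visit for each standard vital sign parameter", plots actual values and change from baseline at each time point, and counts patients by maximum rise and maximum fall from baseline (cut-points 20, 40 and 60 mmHg for systolic and diastolic pressure, 30 bpm for heart rate). Its one output specific to post-dose readings is maximum post-dose heart rate, an absolute value. Nothing in the SAP defines a change from the same day's pre-dose reading, and SAP section 6 (changes from the protocol) does not mention the choice.

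**The concern.** A reading before each dose, followed by serial readings under hospital observation, is a schedule for detecting acute post-dose change. The maximum-change tables do not use that structure. A patient whose pressure drifts down over weeks can be counted as having a large fall without any dosing effect. A patient whose pressure has drifted up can have a large same-day fall that is recorded as small.

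Vital signs are a stated secondary safety endpoint, and the trial has no control arm. The patient's own pre-dose reading is therefore the nearest available reference for an acute effect. At stake is how informative the descriptive safety tables are; no test or decision rule rests on them.

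**Working it through.** The documents give no figure on this point to reproduce, and no SD for blood pressure or heart rate.

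**1. Readings (Protocol 1.3, 6.1 and 8.2.3).** A cycle in the range 1 to 3 has 4 dosing days × (1 pre-dose + 4 post-dose) + 1 day 15 reading = 21 readings. Three cycles give 63: 48 post-dose, 12 pre-dose and 3 on day 15. On cycle 1 day 1 the baseline is normally that day's pre-dose reading (SAP 4.1.2 and 4.1.3), so that day's 4 post-dose changes are already same-day changes. The other 48 − 4 = 44 post-dose readings are compared with a reading from an earlier day. Of the 63 − 1 = 62 readings after baseline, 11 + 3 = 14 (23%) are pre-dose or day 15 readings. SAP 5.6.6 does not bar these from supplying the maximum.

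**2. Identity.** For any post-dose reading:

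SAP change = (same-day pre-dose − baseline) + (post-dose − same-day pre-dose)

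Only the second term is the acute change. Systolic examples in mmHg:

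- Baseline 130, later pre-dose 150, post-dose 112. The same-day fall is 150 − 112 = 38. The SAP change is 112 − 130 = −18, so this reading counts as a fall below 20.
- Drift −15 and acute change −10. The SAP change is −25 (the 20 to under 40 category), although the acute fall is 10.
- Drift +15 and acute change −20. The SAP change is −5, which hides the 20 mmHg acute fall.

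The identity needs no SD assumption.

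**3. Illustrative size.** Simulated reading = day level N(0, between-day SD) + reading error N(0, within-day SD) − true effect (post-dose readings only), over three cycles. All SDs are assumptions. The entries are the share of patients in whom the maximum systolic fall reaches the cut.

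| True fall | Between-day SD | Within-day SD | Cut | Single baseline | Same-day pre-dose |
|---|---|---|---|---|---|
| 0 | 8–12 | 4–6 | ≥20 | about 42–69% | about 1–32% |
| 0 | 8 | 7 (post-dose readings only) | ≥20 | 57% | 57% |
| 0 | 8 | 8 (post-dose readings only) | ≥20 | 63% | 77% |
| 10 | 8–12 | 4–6 | ≥20 | about 78–88% | about 77–99% |
| 10 | 8–12 | 4–6 | ≥40 | about 11–41% | about 0–1% |

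With a true 10 mmHg fall and SDs in the main range, 12 to 21% of patients whose largest same-day fall is at least 20 mmHg are placed in the under-20 class by the SAP rule.

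**4. Dependence on the assumptions.** With within-day SD 5 mmHg, two cycles and no effect, the share with a maximum rise of at least 20 mmHg from the single baseline is 5%, 24%, 42% and 52% for between-day SD 0, 5, 8 and 10 mmHg. From same-day pre-dose it is 6 to 7% throughout. Over four cycles the figures are 7%, 33%, 54% and 64% against 12%. At between-day SD 8 and within-day SD 7, four cycles give 65% against 66%. The single-baseline rate grows with between-day variation. The same-day rate depends on within-day variation and on the number of readings.

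**The case against.** **The tables cannot show an acute effect at all.** A reader might infer this, but it goes too far. SAP 5.6.6 plots values and changes at each time point. For the same patients, the difference between a day's pre-dose and post-dose means is the mean acute change, because the baseline cancels. All readings are also listed, and maximum post-dose heart rate is tabulated. This remedy works for group means only: a patient's extreme in the maximum tables may come from any day and cannot be traced to a dose.

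**The same-day reference is uniformly better.** The working does not support this. A maximum over many differences, each using a noisy pre-dose reading, is inflated under either reference. With a true 10 mmHg fall and within-day SD 5 to 6, the same-day reference puts more patients over the 20 mmHg cut (94–99% against 82–88%).

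**The same-day change should replace the baseline change.** This would lose information. Pre-dose readings on days 2 and 9 follow a dose by about a day. With baseline 130, day 2 pre-dose 110 and post-dose 95, the fall from the untreated state is 35 but the same-day fall is 15. Only the pre-treatment value is drug-free.

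**The same-day change isolates nanrilkefusp alfa.** On days 1 and 8 cetuximab starts within 30 minutes of the injection (Protocol 6.1), so readings after that start reflect the combination.

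**Cytokine release grading is compromised.** Protocol Table 6.4 grades hypotension by response to fluids or need for pressors, not by change in mmHg. Clinically relevant abnormalities are also recorded as adverse events (Protocol 8.3.8.1).

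Change from a pre-treatment baseline is a defensible descriptive choice, and the analyses are descriptive (SAP 5.1). All of this stands. It limits the point to a missing complement and does not remove it.

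**Conclusion.** The concern holds as a gap in the safety description. From cycle 1 day 2, the maximum rise and fall tables in SAP 5.6.6 cannot separate between-day drift from acute post-dose change, although the readings needed to do so are collected on every dosing day. That conclusion follows from the definitions and the identity alone.

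The size is conditional. The 42–69% versus 1–32% contrast rests on assumed SDs, independent day-to-day variation, three cycles and no drug effect. It should be read as an illustration, not as an expected false-positive rate. Where within-day variation is as large as 7 to 8 mmHg with between-day SD 8, the contrast disappears or reverses. Cycle 1 day 1 is normally unaffected.

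**What to change.** In SAP 5.6.6, keep all existing change-from-baseline outputs and add:

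- change from same-day pre-dose, defined as each post-dose reading minus that day's pre-dose reading, summarised by cycle, day and time point;
- the existing maximum rise and fall categories for blood pressure and heart rate, applied to that same-day change.

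State in the text or table footnotes that readings after the cetuximab start on days 1 and 8 reflect the combination, and that day 2 and day 9 pre-dose values are not drug-free.

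The cost is SAP wording, one derived variable and a few extra descriptive tables. No new measurement or protocol amendment is needed.

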8.2.3.2 Nanrilefusp alfa treatment days of cycle 4 and onwards

Patients will be observed in the hospital up to 2 hours after nanrilefusp alfa administration. Vital signs (blood pressure [systolic and diastolic, after ≥ 5 minutes of rest], body temperature, and heart rate) will be documented at the following frequency until discharge:

- Before nanrilefusp alfa administration
- 15 minutes (± 5 minutes) after nanrilefusp alfa administration
- 30 minutes (± 5 minutes) after nanrilefusp alfa administration
- 2 hours (± 15 minutes) after nanrilefusp alfa administration

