4.1.1 Study design

First, 3 patients will be recruited sequentially so that the first administrations of nanrilkefusp alfa to the first and second patients will be 7 days apart and the second and third patients will not be dosed on the same day. These patients will be treated with cetuximab in combination with 9 µg/kg nanrilkefusp alfa, a dose one dose level below the RP2D as determined in study SC103 (AURELIO-03) which evaluated nanrilkefusp alfa at doses up to 12 µg/kg in combination with pembrolizumab. Please see section [6.1](#) for more details on administration of study interventions.

After the last patient in the 9 µg/kg safety cohort completes the first treatment cycle of 21 days, i.e., the DLT assessment period, an internal safety committee (ISC) will review the safety data.

If at least one patient in the initial 9 µg/kg safety cohort experiences a DLT, an additional 3 patients will be recruited into the 9 µg/kg safety cohort. The ISC will review the safety data of these 3 additional patients and decide whether it is safe to increase the dose to 12 µg/kg nanrilkefusp alfa in combination with cetuximab in the second safety cohort or whether the study should proceed with 9 µg/kg nanrilkefusp alfa or with 6 µg/kg nanrilkefusp alfa.

If there are no safety concerns in the initial 9 µg/kg safety cohort, the study will proceed to the second safety cohort and sequentially recruit another 3 patients who will receive 12 µg/kg nanrilkefusp alfa in combination with cetuximab. As in the 9 µg/kg cohort, the first administrations of nanrilkefusp alfa to the first and second patients will be 7 days apart and the second and third patients will not be dosed on the same day. Safety in the 12 µg/kg cohort will be evaluated by the ISC after the last patient completes the DLT assessment period (first treatment cycle of 21 days).

If at least one patient in the 12 µg/kg safety cohort experiences a DLT, an additional 3 patients will be recruited into the 12 µg/kg safety cohort. The ISC will review the safety data of these 3 additional patients and decide whether it is safe to proceed to the main cohort with patients receiving 12 µg/kg nanrilkefusp alfa in combination with cetuximab or whether the study should continue at a lower nanrilkefusp alfa dose.

If there are no safety concerns in the 12 µg/kg safety cohort, the study will proceed to the main cohort and recruit patients who will receive 12 µg/kg nanrilkefusp alfa in combination with cetuximab.

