Patients in the initial 9 µg/kg safety cohort may also have a dose increase to 12 µg/kg nanrilkefusp alfa in the next treatment cycle at the discretion of the investigator if there are no safety concerns in the 12 µg/kg safety cohort.

Patients in the safety cohorts who do not fulfill the DLT evaluability criteria (see section [4.1.3](#)) for any reason other than DLT during the DLT assessment period will be replaced until at least 3 patients per cohort have completed their DLT assessment period.

In the main cohort of the study, patients will be treated with nanrilefusp alfa in combination with cetuximab in 21-day cycles. An independent data monitoring committee (IDMC) will be established to review safety and efficacy data at certain time intervals, or when the interim analysis for futility is triggered, once the main cohort of the study starts.

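### On the planned schedule the optional increase from 9 to 12 µg/kg cannot happen before cycle 4, so the first doses at the higher level fall under the 2-hour observation rule; one sentence would restore the 4-hour rule for that cycle

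*Protocol*

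**What the plan says.** Four parts of the protocol bear on this.

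- **The option to increase (4.1.1).** Patients in the initial 9 µg/kg cohort may go to 12 µg/kg "in the next treatment cycle at the discretion of the investigator if there are no safety concerns in the" higher-dose cohort. SAP 2.1 repeats the option.
- **When that is known (4.1.1).** The 12 µg/kg cohort opens after the internal safety committee (ISC) has reviewed the 9 µg/kg cohort. Safety at 12 µg/kg "will be evaluated by the ISC after the last patient completes the DLT assessment period (first treatment cycle of 21 days"). Each cohort is staggered in two steps. For the opening pair, "the first administrations of nanrilkefusp alfa to the first and second patients will be 7 days apart". For the next pair the rule is only that "the second and third patients will not be dosed on the same day".
- **Observation in cycles 1 to 3 (8.2.3.1).** "Patients will be observed in the hospital up to 4 hours following nanrilefusp alfa administration", with vital signs before dosing and at 15 min, 30 min, 2 h and 4 h.
- **Observation from cycle 4 (8.2.3.2).** "Patients will be observed in the hospital up to 2 hours after nanrilefusp alfa administration", with the same readings except the one at 4 h.

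Note 10 of the schedule of activities ("Before and after nanrilkefusp alfa administration as described in section" 8.2.3) only points back to these two subsections. Protocol 6.5.1 on dose modification and SAP 2.1 add no observation rule for a patient whose dose is raised.

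**The concern.** The switch from 4 h to 2 h depends on the cycle number and not on how long the patient has been at the current dose. If the increase can only come in cycle 4 or later, every patient who takes the option on the planned schedule receives the first 12 µg/kg doses under the shorter rule. Yet the protocol treats 12 µg/kg with cetuximab as a step of its own, with a separate staggered cohort and a separate DLT review.

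What is at stake is safety monitoring of a few patients at a dose new to them. Post-dose cytokine samples are scheduled only in cycles 1 and 2, and pharmacokinetic sampling ends at cycle 3 day 1. From cycle 4 the vital signs of 8.2.3.2 are therefore the main scheduled post-dose check. Protocol 2.3 lists pyrexia and chills among the most common treatment-emergent events, and temperature is part of each reading.

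**Working it through.** The documents state no earliest cycle for the increase, so there is no plan figure to reproduce. The check is calendar arithmetic.

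**Inputs.** Stagger of 7 days, then at least 1 day; DLT period of 21 days; cycle length of 21 days; four nanrilkefusp alfa dosing days per cycle (days 1, 2, 8 and 9); 3 patients planned per safety cohort (all from the protocol). ISC review time and recruitment lag are not given. I assume 0 days, which favours the earliest increase, and test review times up to 21 days per review.

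**Calendar.** Day 0 is the first dose of the first 9 µg/kg patient.

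1. 9 µg/kg starts: 0, 7, 7 + 1 = 8. Cohort complete: 8 + 21 = day 29.
2. 12 µg/kg starts: 29, 29 + 7 = 36, 36 + 1 = 37. Cohort complete: 37 + 21 = day 58.
3. Cycle k day 1 = start + 21 × (k − 1). The increase can begin at the first such date on or after day 58.

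| 9 µg/kg start | Cycle 3 day 1 | Cycle 4 day 1 | Slip needed to increase in cycle 3 |
|---|---|---|---|
| 0 | 42 | 63 | 58 − 42 = 16 days |
| 7 | 49 | 70 | 58 − 49 = 9 days |
| 8 | 50 | 71 | 58 − 50 = 8 days |

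All three are past cycle 3 day 1 by day 58, so cycle 4 is the earliest. The result does not depend on who starts last. Clearance comes at least 21 + 8 + 21 = 50 days after the last 9 µg/kg start, against 42 days to cycle 3 day 1, so it also covers a replacement patient.

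**Sensitivity.**

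| Change | Clearance | Earliest cycle for the three patients |
|---|---|---|
| DLT period counted as 20 days | 56 | 4, 4, 4 (slip needed for cycle 3: 14, 7, 6 days) |
| 20-day count and each cycle 1 day late | 56 | 4, 4, 4 |
| Review time 3 days each | 64 | 5, 4, 4 |
| Review time 7 days each | 72 | 5, 5, 5 |
| Review time 14 days each | 86 | 6, 5, 5 |
| Review time 21 days each | 100 | 6, 6, 6 |
| 12 µg/kg cohort expanded (58 + 21) | 79 | 5, 5, 5 |
| 9 µg/kg cohort expanded (29 + 21 = 50; 12 µg/kg starts 50, 57, 58; 58 + 21) | 79 | 5, 5, 5 |

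Every realistic delay moves the increase later, still under the 2 h rule.

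**Difference in monitoring in the first cycle at 12 µg/kg, per escalated patient.**

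- Post-dose readings: 4 per dosing day under 8.2.3.1 against 3 under 8.2.3.2. Over 4 dosing days, 4 × 4 = 16 against 3 × 4 = 12, so at most 4 fewer.
- Observation: (4 − 2) × 4 = at most 8 h less.
- For 0, 1, 2 or 3 patients: at most 0, 4, 8 or 12 fewer readings and at most 0, 8, 16 or 24 fewer hours.

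These are maxima because both subsections say up to a given time and document vital signs until discharge.

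**Earlier exposure.** Before a cycle 4 increase the patient has had 3 × 4 = 12 planned dosing days at 9 µg/kg, all under the 4 h rule.

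**The case against.** The strongest reply is that a rule by cycle number is a sensible rule by experience with the drug. An escalated patient has tolerated about 12 dosing days one dose level below, and 12 µg/kg was already the recommended dose in the sponsor's earlier phase 1/1b study. The increase also requires that the 12 µg/kg cohort raised no safety concerns. Under 8.2.3.2 the patient keeps readings before dosing and at 15 min, 30 min and 2 h, and returns on days 2 and 9 for pre-dose vital signs about 24 h after the day 1 and day 8 doses. The investigator chooses whether to raise the dose and may observe for longer. The ISC Charter and the Investigator's Brochure, which are not among the documents reviewed, might add guidance.

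Most of this stands, and it limits the benefit. It does not remove the point: longer observation is left to individual judgement, and in the protocol and SAP no rule links observation to a dose increase.

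A reader might go further and say that escalated patients are treated worse than the main cohort, who start 12 µg/kg after the same clearance ("safety cohort, the study will proceed to the main cohort and recruit patients who will receive" 12 µg/kg) and have the 4 h rule for three cycles. That comparison overstates the gap. Main-cohort patients are new to the drug, whereas escalated patients are new only to the dose. It supports one cycle at 4 h, not three.

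**Conclusion.** The gap is real but small. On the planned schedule the increase cannot come before cycle 4, and the first 12 µg/kg doses of an escalated patient then fall under the 2 h rule. The cost to each such patient is at most 8 h of observation and 4 readings in that cycle.

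The assumptions are these:

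- Cycles run on schedule. Only a slip of 8 to 16 days (6 to 14 on a 20-day DLT count) would bring the increase into cycle 3.
- Zero review and recruitment lag, which is the case most favourable to an early increase.
- The number affected starts at 0, because the increase is optional. Three is the planned cohort size and not a firm ceiling, since non-evaluable patients are replaced. Section 4.1.1 also does not say whether patients added after a DLT count as part of the initial cohort.

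A reader might infer that 2 h of observation is unsafe at 12 µg/kg. The documents do not show that: nothing in them places the risk between 2 and 4 h, and the only post-dose cytokine sample is at 6 h, outside both windows. Nor is any result of the trial at risk. The DLT period is cycle 1, the futility rule counts tumour responses, and no endpoint definition changes. This is an optional, inexpensive improvement.

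**What to change.** Add one sentence to Protocol 8.2.3:

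> The assessments of 8.2.3.1 (observation and vital signs to 4 hours) also apply on all nanrilkefusp alfa treatment days of the first cycle given at an increased dose, whatever its cycle number.

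Cross-refer to it from the dose-increase sentence in 4.1.1 and from note 10 of the schedule of activities. One cycle is enough, because these patients are new to the dose but not to the drug.

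The cost is at most 2 extra hours and one extra reading on each of 4 dosing days per escalated patient. For 3 patients that is at most 3 × 8 = 24 hours and 3 × 4 = 12 readings. No extra visits or blood samples are needed, and the statistical analysis is unchanged.
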